### *8.6.2. Annual progress report*

The coordinating investigator will submit a summary of the progress of the study to the accredited institutional review board (IRB) once a year. Information will be provided on the date of inclusion of the first subject, numbers of subjects included and numbers of subjects that have completed the study, serious adverse events/ serious adverse reactions, other problems, and amendments.

#### *8.6.3. End of study report*

The investigator will notify the accredited IRB of the end of the study within a period of 8 weeks. The end of the study is defined as the last patient's last follow-up visit. In case the study is ended prematurely, the investigator will notify the accredited IRB within 15 days, including the reasons for the premature termination. Within one year after the end of the study, the investigator/sponsor will submit a final study report with the results of the study, including any publications/abstracts of the study, to the accredited IRB.

#### *8.6.4. Public disclosure and publication policy*

The results of this study will be disclosed unreservedly according to the Central Committee on Research Involving Human Subjects (CCMO) statement on publication policy (<http://www.ccmo.nl/attachments/files/ccmo-statement-publicatiebeleid-3-02-en.pdf>).

#### *8.6.5. Monitoring and Quality Assurance*

Monitoring in all sites in the Netherlands will be executed by (internal) monitors of the LUMC according to the monitor plan.

### **8.7 Insurance**

The sponsor has a liability insurance which is in accordance with article 7 of the WMO. The sponsor (also) has an insurance which is in accordance with the legal requirements in the Netherlands (Article 7 WMO and the Measure regarding Compulsory Insurance for Clinical Research in Humans of 2015).. This insurance provides cover for damage to research subjects through injury or death caused by the study:

- 1) € 650.000,-- (i.e. six hundred and fifty thousand Euro) for death or injury for each subject who participates in the Research;
- 2) € 5.000.000,-- (i.e. five million Euro) for death or injury for all subjects who participate in the Research;
- 3) € 7.500.000,-- (i.e. seven million five hundred thousand Euro) for the total damage incurred by the organisation for all damage disclosed by scientific research for the Sponsor as 'verrichter' in the meaning of said Act in each year of insurance coverage. The insurance applies to the damage that becomes apparent during the study or within 4 years after the end of the study.

## **9. Safety reporting**

### **9.1 Section 10 WMO event**

In accordance to section 10, subsection 1, of the WMO, the investigator will inform the subjects and the reviewing accredited METC if anything occurs, on the basis of which it appears that the disadvantages of participation may be significantly greater than was foreseen in the research proposal. The study will be suspended pending further review by the accredited METC, except insofar as suspension would jeopardise the subjects' health. The investigator will take care that all subjects are kept informed.

### **9.2 Adverse events**

Adverse events are defined as any suspected recurrent venous thromboembolism occurring to a subject during the study. All adverse events reported spontaneously by the subject or observed by the investigator or his staff will be recorded.

### **9.3 Serious adverse events**

A serious adverse event is an objectively proven (fatal) PE or death. The investigator will report all (fatal) PEs and deaths to the sponsor without undue delay after obtaining knowledge of the events.

The sponsor will report the (fatal) PEs and deaths through the web portal *ToetsingOnline* to the accredited METC that approved the protocol, within 7 days of first knowledge for the (fatal) PE and deaths followed by a period of maximum of 8 days to complete the initial preliminary report.

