## Study schedule

	Visit 0: Clinical assessment	Visit 1: Enrolment	Visit 2: MRDTI (within 48 hours of visit 1 in acute SVT)	Visit 3: 90-day follow-up
Check for inclusion/exclusion criteria		X		
Obtain informed consent		X		
Medical history		X		
Demographic data		X		
Clinical examination		X		
Laboratory test (D-dimer, renal function)		X*		
Doppler ultrasound, CT or MRI of the abdomen	X*			
Treatment decision	X			
MRDTI of abdomen			X	
Recording of				
Death				X
Major bleeding				X
Hospital admission				X
Symptomatic SVT or VTE				X

\*Part of clinical practice, no study proceedings

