## 1. Introduction and hypothesis

Compared to lower extremity deep vein thrombosis (DVT) and pulmonary embolism (PE), very little research has focused on the diagnostic management of splanchnic vein thrombosis (SVT).[3] The tests that are currently used to diagnose SVT, doppler ultrasound (DUS) and computed tomography angiography (CTA), have a number of limitations, particularly related to patient safety. For example, CT angiography involves the use of ionizing radiations and iodinated contrast agent, with potential renal toxicity or allergic reactions. DUS has the advantage of being relatively inexpensive and widely available. It is however operator-dependent and the accuracy can be limited by body habitus and the presence of intestinal gas.[3] Importantly, whereas the diagnosis of symptomatic SVT is often challenging, the correct diagnosis of acute versus chronic SVT is even more difficult, as neither of the current available imaging tests is helpful in determination of the age of the thrombus or its clinical relevance. Due to this impossibility to determine whether the incidentally observed thrombosis is acute, chronic or even an imaging artefact, the vast majority of patients with incidental SVT are treated with -often lifelong- anticoagulants. It is widely acknowledged that this practice likely results in overdiagnosis and unjust exposure to anticoagulant therapy with associated risk of bleeding. In the proposed study we will evaluate whether magnetic resonance direct thrombus imaging (MRDTI) is a valid, reliable, safe and effective alternative for the diagnosis of acute and chronic SVT. Our primary hypothesis is that MRDTI will demonstrate acceptable sensitivity and specificity for the diagnosis of acute SVT and the differentiation between acute and chronic SVT.

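### The adverse event definitions leave out non-fatal harm from the MRDTI scan and do not classify the major bleeding and hospital admissions recorded at day 90

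*Combined protocol and SAP*

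**What the plan says.** Section 9.2: "Adverse events are defined as any suspected recurrent venous thromboembolism occurring to a subject during the study".

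Section 9.3: "A serious adverse event is an objectively proven (fatal) PE or death". The reporting duty has the same scope: "The investigator will report all (fatal) PEs and deaths to the sponsor without undue delay after obtaining knowledge of the events".

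The study schedule lists four items to record at visit 3 (90-day follow-up): death, "Major bleeding", "Hospital admission", and symptomatic SVT or VTE. It lists no safety item at visit 2, when the MRDTI is done.

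Section 1 says the study will evaluate whether MRDTI "is a valid, reliable, safe and effective alternative for the diagnosis of acute and chronic SVT".

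Two other provisions bear on safety. Section 9.1 requires notice to subjects and the ethics committee, and suspension pending review, when it appears that "the disadvantages of participation may be significantly greater than was foreseen in the research proposal". Section 8.6.2 promises the review board a yearly report that covers serious adverse events, serious adverse reactions and other problems.

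**The concern.** Both definitions are closed lists, and no other section widens them. They cover thrombotic events and death, which come mainly from the underlying disease. They leave out the events that the study procedure itself could cause: intolerance, injury or any other untoward event during or after the scan. Such problems are foreseeable, because Section 5.3 excludes patients with MRI contraindications, claustrophobia or inability to lie flat. Screening can miss some of them.

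Three things are at stake. First, the protocol requires no scan harm to be recorded as such, and the duty in Section 9.4 to follow adverse events to resolution does not reach it. Second, the schedule collects non-fatal bleeding and admissions, but Section 9 gives them no status and no analysis uses them. Third, a later report that no scan-related adverse events occurred would say little, because the definitions exclude nearly all of them.

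**Working it through.** The check is mainly textual. The plan gives no safety figure to reproduce.

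**Step 1. Each kind of event against the definitions.**

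| Event | Recorded at a scheduled visit | AE (9.2) | SAE (9.3) |
|---|---|---|---|
| Suspected recurrent VTE | Visit 3, if symptomatic | Yes | Only if a proven PE or fatal |
| Death from any cause, including a fatal bleed | Visit 3 | Only if suspected VTE | Yes |
| Non-fatal major bleeding | Visit 3 | No | No |
| Admission without suspected VTE | Visit 3 | No | No |
| Non-fatal scan harm that leads to admission | Visit 3, as an admission | No | No |
| Other non-fatal scan harm | No | No | No |

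The last two rows are the main gap. The two rows above them are a mismatch between the schedule and Section 9. Those events are collected, but nothing is done with them.

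**Step 2. Is the scan the relevant exposure?** The schedule marks the diagnostic imaging and laboratory tests as clinical practice. Section 4.4 says that diagnosis and treatment plan are settled before inclusion and that MRDTI findings do not influence them. The scan is therefore the main thing that participation adds.

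**Step 3. Is safety analysed anywhere?** The endpoints are sensitivity and specificity (6.1), and scan sequences and interobserver agreement (6.2). Sections 7.2.1 and 7.2.2 analyse only these. No safety summary is planned.

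**Step 4. Do other routes close the gap?** Section 9.1 applies only when disadvantages appear significantly greater than foreseen. It is a rule for escalation and gives no routine capture. Section 8.6.2 mentions other problems without saying what belongs there. It also mentions serious adverse reactions, which Section 9 never defines.

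**Step 5. What could recorded scan events show?** Planned enrolment is 3 + 35 + 35 = 73 to 5 + 35 + 35 = 75. Assume that every patient is scanned. With zero events, the upper limit of the exact two-sided 95% interval is 1 − 0.025^(1/n):

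- n = 73: 1 − 0.025^(1/73) = 0.0493, or 4.9%
- n = 75: 1 − 0.025^(1/75) = 0.0480, or 4.8%

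The chance of at least one event among 75 patients is 1 − (1 − p)^75. The documents give no value for p, so the rates below are assumptions:

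| Assumed true rate p | Chance of at least one event |
|---|---|
| 1% | 1 − 0.99^75 = 53% |
| 2% | 1 − 0.98^75 = 78% |
| 5% | 1 − 0.95^75 = 98% |

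A study of this size could give a modest descriptive statement about scan harm, but only if the events are recorded.

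**The case against.** Narrow, disease-specific definitions can be a proportionate choice for one scan of 8–12 minutes without contrast (4.3, 2.4.1), with MRI contraindications excluded and no effect on management. Bleeding and admissions would mostly reflect the disease and usual care. Safety appears as an aim only in the introduction, where the contrast is with radiation and contrast agents; it is absent from the objectives and endpoints. All of this is fair, and it limits the weight of the point. It does not explain why the one study procedure has no event capture, and the protocol gives no reason for the narrow lists.

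A reader might infer more than the documents support, in three ways.

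- *That bleeding, admissions and scan harm never reach the sponsor or ethics committee.* Bleeding and admissions are collected at day 90, and coded data go to the sponsor (7.3.1). A fatal bleed is reported as a death. A grave scan injury could trigger 9.1, and 8.6.2 leaves a discretionary annual route.
- *That the number of missed bleeds can be estimated from the 25% in Section 2.3.* That figure is for gastrointestinal bleeding in acute PVT or SpVT shortly after anticoagulation began. The study's acute group also admits other sites, the schedule records major bleeding, and treatment is decided before enrolment, so some early bleeds may precede it. The figure does not measure this gap.
- *That every hospital admission should become a serious adverse event.* In a population with oncologic, post-surgical and inflammatory or infectious risk factors, this could put many disease-related admissions on the 7-day route in 9.3. The mismatch can be resolved without it.

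**Conclusion.** The point holds in a limited form. Under Sections 9.2 and 9.3, non-fatal harm from the scan is not an adverse event unless it is suspected VTE. The non-fatal major bleeding and admissions recorded at visit 3 are not classed, reported or summarised as safety events. The remaining routes are partial and discretionary. The word safe in Section 1 has no planned data behind it.

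The effect is on safety capture and on what may be claimed; the sensitivity and specificity estimates are untouched. With recording in place and no events, the data could exclude scan-harm rates above about 5% (4.9% at n = 73, 4.8% at n = 75), assuming that all enrolled patients are scanned. The conclusion rests on reading the two definitions as exhaustive, and nothing in the protocol suggests otherwise. It is an inexpensive improvement that the sponsor should make.

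**What to change.** 1. Extend Section 9.2 to any untoward event during the MRDTI procedure or related to it, and add one CRF item at visit 2 to record it.
2. In Section 9.3, class a serious scan-related event as a serious adverse event, and state the criteria for serious.
3. Reconcile the schedule with Sections 9.2 and 9.3: list the non-fatal major bleeding and hospital admissions already collected in the annual report under 8.6.2, without expedited reporting.
4. Add a descriptive summary of scan-related events to Section 7.2 (count, proportion and exact 95% interval), or delete the word safe from Section 1.

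The cost is a few sentences, one CRF item, and slightly more recording and reporting work. Visit 3 needs no new data collection, and the sample size, primary analysis and patient management do not change.

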### **9.4 Follow-up of adverse events**

All AEs will be followed until they have abated, or until a stable situation has been reached.

Depending on the event, follow up may require additional tests or medical procedures as indicated, and/or referral to the general physician or a medical specialist. SAEs need to be reported till end of study within the Netherlands, as defined in the protocol.

## **10. Agreements**

### **10.1 Financing of the study**

This study is supported by an unrestricted grant from the International Society on Thrombosis and Haemostasis (ISTH).

### **10.2 Publication**

Any publication of the results, either in part or in total (articles in journals or newspapers, oral presentation, etc.) by the investigators or their representatives, shall require the approval of the

principal investigators. It is planned to publish the results of the study as an original article in an appropriate medical journal as well as to present the results at international congresses. The choice of the journal for the publication will be made by the principal investigators in agreement with the co-authors. Besides the principal investigators, further authors of this article must meet the following criteria:

- Substantial contribution to the recruitment of subjects, i.e. inclusion of at least 5 study subjects;
- Substantial contribution to the interpretation of the data;
- Substantial contribution to drafting the article or revising it for intellectual content

